## LIST OF ABBREVIATIONS

ACR	American College of Rheumatology
ACR 20/50/70	American College of Rheumatology 20/50/70% improvement
AE	adverse event
ALT	alanine aminotransferase
AST	aspartate aminotransferase
ATC	anatomical therapeutic chemical drug class
AUC	area under the curve
bDMARD	biological disease modifying anti-rheumatic drug
BLQ	below the limit of quantitation
BMI	body mass index
BPM	beats per minute
CDAI	clinical disease activity index
CI	confidence interval
CMH	Cochran-Mantel-Haenszel
CRF	case report form
CRP	C-reactive protein
CPK	creatinine phosphokinase
CSR	clinical study report
CTCAE	common terminology criteria for adverse events
DAS28	disease activity score for 28 joint count
ECG	electrocardiogram
eCRF	electronic case report form
FAS	full analysis set
Gilead	Gilead Sciences
HAQ-DI	health assessment questionnaire-disability index
HLGT	high-level group term
HLT	high-level term
ID	identification
IXRS	interactive web and mobile response system
JAK	janus kinase
LLOQ	lower limit of quantitation
LLT	lower-level term
LOCF	last observation carried forward
LOQ	limit of quantitation
MedDRA	medical dictionary for regulatory activities
MMRM	mixed model repeated measures
MTX	methotrexate
NRI	non-responder imputation

---

PhGA	physician's global assessment
PT	preferred term
PtGA	patient's global assessment
PK	pharmacokinetic
POC	proof-of-concept
PTM	placebo-to-match
Q1, Q3	first quartile, third quartile
QD	quaque die (each day)
QT	electrocardiographic interval between the beginning of the Q wave and termination of the T wave, representing the time for both ventricular depolarization and repolarization to occur
QTc	corrected QT
QTcF	corrected CT interval using the Fridericia formula
RA	rheumatoid arthritis
SAE	serious adverse event
SAP	statistical analysis plan
SD	standard deviation
SDAI	simplified disease activity index
SE	standard error
SJC	swollen joint count
SOC	system organ class
SYK	spleen tyrosine kinase
TE	treatment-emergent
TEAE	treatment-emergent adverse event
TFs	tables, figures, and listings
TJC	tender joint count
ULN	upper limit of normal
VAS	visual analog scale
WHO	World Health Organization

## PHARMACOKINETIC ABBREVIATIONS

$AUC_{\text{tau}}$	area under the concentration versus time curve over the dosing interval
$C_{\text{last}}$	last observed quantifiable concentration of the drug
$C_{\text{max}}$	maximum observed concentration of drug
$C_{\text{tau}}$	observed drug concentration at the end of the dosing interval
$CL_{\text{ss}}/F$	apparent oral clearance after administration of the drug: at steady state: $CL_{\text{ss}}/F = \text{Dose}/AUC_{\text{tau}}$ , where “Dose” is the dose of the drug
$t_{1/2}$	estimate of the terminal elimination half-life of the drug, calculated by dividing the natural log of 2 by the terminal elimination rate constant ( $\lambda_z$ )
$T_{\text{last}}$	time (observed time point) of $C_{\text{last}}$
$T_{\text{max}}$	time (observed time point) of $C_{\text{max}}$
$V_z/F$	apparent volume of distribution of the drug
$\lambda_z$	terminal elimination rate constant, estimated by linear regression of the terminal elimination phase of the concentration of drug versus time curve

## 1. INTRODUCTION

This statistical analysis plan (SAP) describes the statistical analysis methods and data presentations to be used in tables, figures, and listings (TFLs) in the clinical study report (CSR) for study GS-US-379-1582. This SAP is based on the study protocol amendment 2 dated 11 July 2016 and the electronic case report form (eCRF). The SAP will be finalized before database finalization. Any changes made after the finalization of the SAP will be documented in the CSR.

### 1.1. Study Objectives

The primary objective of this study is as follows:

- To evaluate the effect of GS-9876 versus placebo for the treatment of signs and symptoms of rheumatoid arthritis (RA) in subjects with active RA as measured by change from baseline in disease activity score for 28 joint count using the C-reactive protein (CRP) (DAS28[CRP]) at Week 12

The secondary objectives of this study are as follows:

- To evaluate the safety and tolerability of GS-9876 in subjects with RA
- To explore the effect of GS-9876 on other disease-specific outcomes in RA

The exploratory objectives of this study are as follows:

PPD [REDACTED]  
[REDACTED]  
[REDACTED]  
[REDACTED]

[figure not shown]
### 1.2. Study Design

This is a randomized, double-blind, placebo-controlled, Phase 2 proof-of-concept (POC) study evaluating the safety, tolerability, and efficacy of GS-9876 in adult male and female subjects with active RA despite MTX therapy who had an inadequate response to MTX (either alone or in combination with biological disease modifying anti-rheumatic drug [bDMARD]). In addition, the effect of GS-9876 and filgotinib on disease and/or pathway markers relevant to RA and/or the SYK and JAK pathways will be assessed.

A total of approximately 80 subjects will be randomized in this study. The study design is shown in [Figure 1-1](#).

**Figure 1-1.**

**Study Schema**

Following completion of screening assessments, eligible subjects will be randomized in a blinded fashion in a 1:1:1:1 ratio as follows (all groups will continue to take MTX):

- GS-9876 30 mg:** GS-9876 (1 x 30 mg tablet QD) + placebo-to-match (PTM) filgotinib (2 x placebo tablets QD) (N=20)
- GS-9876 10 mg:** GS-9876 (1 x 10 mg tablet QD) + PTM filgotinib (2 x placebo tablets QD) (N=20)
- Filgotinib 200 mg:** Filgotinib (2 x 100 mg tablets QD) + PTM GS-9876 (1 x placebo tablets QD) (N=20)
- Placebo only:** PTM GS-9876 (1 x placebo tablet QD) + PTM filgotinib (2 x placebo tablets QD) (N=20)

Randomization will be stratified by prior inadequate response to biologic therapy and geographic region.

Subjects will be dosed for up to 12 weeks and then followed for 4 weeks after their last dose of study drug.

### 1.3. Sample Size and Power

Sample sizes for GS-9876 and placebo groups are determined based on the superiority test of 1 dose of GS-9876 compared to placebo based on the change from baseline in DAS28(CRP) at Week 12. When assuming a difference of 1.2 between the 2 groups and a common standard deviation of 1.35, 20 subjects in each of the GS-9876 groups and 20 in the placebo group are required to obtain 78% power at a 2-sided 0.05-level. **PPD**

. Therefore, the total sample size will be 80 (20 per treatment group).

## **2. TYPE OF ANALYSIS**

### **2.1. Interim Analyses**

Administrative interim analyses of efficacy and safety data were performed by the Gilead internal unblinded team. The purpose of the analyses was to assess efficacy of GS-9876 for further planning and development as a single agent and in combination. This unblinded team was independent of the GS-US-379-1582 study team who were not directly involved in routine study conducts. People who were unblinded were documented in the unblinded form GF-27011A, and the justification was documented in GT-27011A per SOP-BM-27011. The Study Team has remained blinded to treatment assignments throughout the trial until all subjects have completed the planned study visits and the database has been locked and unblinded.

### **2.2. Final Analysis**

After all subjects have completed the study, outstanding data queries have been resolved or adjudicated as unresolvable, and the data have been cleaned and finalized, the study blind will be broken and the final analysis of the data will be performed.

### **3. GENERAL CONSIDERATIONS FOR DATA ANALYSES**

Analysis results will be presented using descriptive statistics. For categorical variables, the number and percentage of subjects in each category will be presented; for continuous variables, the number of subjects (n), mean, standard deviation (SD) or standard error (SE), median, first quartile (Q1), third quartile (Q3), minimum and maximum will be presented.

All statistical tests will be 2-sided and performed at the 5% significance level unless otherwise specified.

By-subject listings will be presented for all subjects in the All Randomized Analysis Set and sorted by treatment group, site/investigator identification (ID) number, subject ID number, visit date, and time (if applicable). Data collected on log forms, such as AEs, will be presented in chronological order within the subject. The treatment group to which subjects were randomized will be included in the listings, as well as age, sex at birth, race, and ethnicity.

#### **3.1. Analysis Sets**

Analysis sets define the subjects to be included in an analysis. Analysis sets and their definitions are provided in this section. The analysis set will be identified and included as a subtitle of each TFL.

For each analysis set, the number and percentage of subjects eligible for inclusion, as well as the number and percentage of subjects who were excluded and the reasons for their exclusion, will be summarized by treatment group.

A listing of reasons for exclusion from analysis sets will be provided by subject.

##### **3.1.1. All Randomized Analysis Set**

All Randomized Analysis Set includes all subjects who are randomized in the study. This is the primary analysis set for by-subject listings.

##### **3.1.2. Full Analysis Set**

The Full Analysis Set (FAS) includes all randomized subjects who received at least 1 dose of study drug. The study drugs in this study are filgotinib, GS-9876, and PTMs for GS-9876 or filgotinib. This is the primary analysis set for efficacy analyses.

##### **3.1.3. Safety Analysis Set**

The Safety Analysis Set includes all subjects who received at least 1 dose of study drug. This is the primary analysis set for safety analyses.

### **3.1.4. Pharmacokinetic Analysis Set**

The pharmacokinetic (PK) analysis set includes all subjects in the Safety Analysis Set who have at least 1 nonmissing PK concentration data for GS-9876, filgotinib and/or their metabolites. This is the primary analysis set for general PK analyses.

### **3.1.5. Pharmacokinetic Substudy Analysis Set**

The PK Substudy Analysis Set includes all subjects in the Safety Analysis Set who have enrolled into the PK Substudy, and have intensive PK concentration data to provide interpretable results for the specific parameters of interest for the analyte under evaluation. This is the primary analysis set for intensive PK analyses.

## **3.2. Subject Grouping**

For analyses based on the All Randomized Analysis Set or FAS, subjects will be grouped according to the treatment to which they were randomized. For analyses based on the Safety Analysis Set, subjects will be grouped according to actual treatment received. The actual treatment received will differ from the randomized treatment only when their actual treatment differs from randomized treatment for the entire treatment duration.

For the PK Analysis Set, subjects will be grouped according to the actual treatment they received.

## **3.3. Strata and Covariates**

Subjects will be randomly assigned to treatment groups via the IXRS in a 1:1:1:1 ratio using a stratified randomization schedule. Stratification will be based on the following variables:

- Geographic region (**Region 1** includes the United States; **Region 2** includes the following countries: Bulgaria, Ukraine, Czech Republic, Georgia, Hungary, Moldova, and Poland)
- Prior inadequate response to biologic therapy (Yes or No). In the eCRF data, subjects who discontinued prior RA biologic therapy before the first dose date of any study drug due to any of the following reasons are considered to have prior inadequate response to biologic therapy:
  - Primary inadequate response
  - Loss of response
  - Intolerance (Non-allergic)
  - Allergic response

Please refer to [Appendix 2](#) for the RA biologic therapy list.

If there are discrepancies in stratification factor values between the IXRS and the clinical database, the values derived from the clinical database will be used for analyses.

For efficacy endpoints, the baseline value of the efficacy variable(s) will be included as covariates in the efficacy analysis model, as specified in Section 6.

### **3.4. Examination of Subject Subgroups**

Subgrouping of subjects based on stratification factors and Arensia sites will be explored for subgroup analyses.

The primary efficacy endpoint and the secondary endpoint of ACR20/50/70 will be examined using the following subgroups:

- Geographic region (Region 1, Region 2, as listed in Section 3.3)
- Prior inadequate response to biologic therapy (Yes, No, as defined in Section 3.3).
- Arensia sites and non-Arensia sites. The Arensia site numbers are 13632 and 13455.

If the number of subjects in a subgroup is not sufficient for modeling-based statistical analyses between treatment groups, descriptive statistics for each treatment group within the corresponding subgroup will be provided instead.

### **3.5. Missing Data and Outliers**

#### **3.5.1. Missing Data**

In general, missing data will not be imputed unless methods for handling missing data are specified. Exceptions are presented in this document.

For missing last dosing date of study drug, imputation rules are described in Section 4.2.1. The handling of missing or incomplete dates for AE onset is described in Section 7.1.5.2, and for prior and concomitant medications in Section 7.4. Imputation rules adopted in the efficacy analyses are specified in Section 6. The handling of missing data for PK is described in Section 8.

#### **3.5.2. Outliers**

Outliers will be identified during the data management and data analysis process, but no sensitivity analyses will be conducted. All data will be included in the data analyses.

### **3.6. Data Handling Conventions and Transformations**

In general, age (in years) on the date of the first dose of study drug will be used for analyses and presentation in listings. If an enrolled subject was not dosed with any study drug, the randomization date will be used instead of the first dosing date of study drug. For screen failures,

the date the last informed consent was signed will be used for age calculation. If only birth year is collected on the case report form (CRF), “01 January” will be used for the unknown birth day and month for the purpose of age calculation. If only birth year and month are collected, “01” will be used for the unknown birth day.

Non-PK Data that are continuous in nature but are less than the lower limit of quantitation (LOQ) or above the upper LOQ will be imputed as follows:

- A value that is 1 unit less than the LOQ will be used to calculate descriptive statistics if the datum is reported in the form of “ $< x$ ” (where x is considered the LOQ). For example, if the values are reported as  $< 50$  and  $< 5.0$ , values of 49 and 4.9, respectively, will be used to calculate summary statistics. An exception to this rule is any value reported as  $< 1$  or  $< 0.1$ , etc. For values reported as  $< 1$  or  $< 0.1$ , a value of 0.9 or 0.09, respectively, will be used for calculate summary statistics.
- A value that is 1 unit above the LOQ will be used to calculate descriptive statistics if the datum is reported in the form of “ $> x$ ” (where x is considered the LOQ). Values with decimal points will follow the same logic as above.
- The LOQ will be used to calculate descriptive statistics if the datum is reported in the form of “ $\leq x$ ” or “ $\geq x$ ” (where x is considered the LOQ).

Natural logarithm transformation will be used for plasma/blood concentrations and analysis of PK parameters. Plasma concentration values that are below the limit of quantitation (BLQ) will be presented as “BLQ” in the concentration data listing. Values that are BLQ will be treated as 0 at predose time points, and one-half the value of the LOQ at postbaseline time points.

The following conventions will be used for the presentation of summary and order statistics:

- If at least 1 subject has a concentration value of BLQ for the time point, the minimum value will be displayed as “BLQ”.
- If more than 25% of the subjects have a concentration data value of BLQ for a given time point, the minimum and Q1 values will be displayed as “BLQ”.
- If more than 50% of the subjects have a concentration data value of BLQ for a given time point, the minimum, Q1, and median values will be displayed as “BLQ”.
- If more than 75% of the subjects have a concentration data value of BLQ for a given time point, the minimum, Q1, median, and Q3 values will be displayed as “BLQ”.
- If all subjects have concentration data values of BLQ for a given time point, all order statistics (minimum, Q1, median, Q3, and maximum) will be displayed as “BLQ”.

PK parameters that are BLQ will be imputed as one-half LOQ before log transformation or statistical model fitting.

### **3.7. Analysis Visit Windows**

#### **3.7.1. Definition of Study Day**

The first dose date of individual study drug will be calculated separately for each study drug (ie, GS-9876, filgotinib, and PTMs) in a treatment group. Study Day 1 is defined as the first dose date of any study drug, which is the minimum of the first dose dates of individual study drugs in a treatment group.

The last dose date of individual study drug will be calculated separately for each study drug in a treatment group. The last dose date for an individual study drug will be the end date on study drug administration CRF for the record where the “study drug was permanently withdrawn” flag is “Yes”. The last dose date of any study drug will be defined as the maximum of the last dose dates of individual study drugs in a treatment group.

Study Day will be calculated from the Study Day 1 and derived as follows:

- For postdose study days: Assessment Date – Study Day 1 + 1
- For days prior to the first dose: Assessment Date – Study Day 1

#### **3.7.2. Analysis Visit Windows**

Subject visits may occur on days not specified in the protocol (eg, unscheduled visits). Therefore, for the purpose of analysis, observations will be assigned to analysis windows.

In general, the baseline value will be the last nonmissing value on or prior to the first dose date of study drug.

**Table 3-1 Analysis Visit Windows for Joint Count Assessment, HAQ-DI, PhGA, PtGA, and On-Treatment CRP, Safety Laboratory Data, Weight, Vital Signs, ECG**

Nominal Visit	Nominal Study Day	Lower Limit	Upper Limit
Baseline	1	(none)	1
Week 2	15	2	22
Week 4	29	23	43
Week 8	57	44	71
Week 12	85	72	≥ 85

The analysis windows for joint count assessment, health assessment questionnaire - disability index (HAQ-DI) (including the patient’s assessment of pain), physician’s global assessment of disease activity (PhGA), patient’s global assessment of disease activity (PtGA), on-treatment CRP, safety laboratory, weight, vital signs and electrocardiogram (ECG) are provided in [Table 3-1](#). CRP, safety laboratory, weight, vital signs, and ECG data collected up to the last dose date of any study drug + 3 days are considered to be on-treatment data.

CRP, safety laboratory, weight, vital signs, and ECG data collected after last dose date of any study drug + 3 days will be considered as posttreatment data and will be summarized up to last dose date plus 30 days, and labeled as “FU-Week 4”. Data obtained after last dose date plus 30 days will be excluded from the summaries, but will be included in the listings.

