## 6. EFFICACY ANALYSES

### 6.1. General Considerations

The primary analysis set for efficacy analyses will be the FAS, defined in Section 3.1.2.

If multiple valid, nonmissing efficacy measurements exist in an analysis window, records will be chosen based on the following rules if a single value is needed:

- If record collection date/time is known, latest record will be taken
- If time is unknown, the worst scenario will be selected

For the composite endpoints including DAS28(CRP), ACR 20/50/70, SDAI, and CDAI, we use the following steps unless otherwise specified:

- Step 1: Put each component value into a visit window
- Step 2: Within each visit window, select the component data point for analysis
- Step 3: Combine these selected data points within each visit window across the components.

Below are the descriptions for the imputation methods that will be used throughout the efficacy analyses:

- Observed case (OC): missing values remain missing. For the above composite endpoints, in the case that some components are missing, the composite endpoint assessment will be derived based on the non-missing components. If non-missing components are not sufficient to determine final composite endpoint, then the composite endpoint will be considered as missing.
- Last observation carried forward (LOCF): For the above composite endpoints, First LOCF all components over all visits, then combine the components as mentioned above.
- Non-responder imputation (NRI): For all binary response measurements, starting from OC, all missings will be treated as non-responders.

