**DAS28(CRP) = 0.56 $\sqrt{\text{TJC28}}$  + 0.28 $\sqrt{\text{SJC28}}$  + 0.36 ln(CRP + 1) + 0.014 × PtGA + 0.96,**  
where

TJC28 = number of joints tender out of 28 joints

SJC28 = number of joints swollen out of 28 joints

CRP = CRP measurement in unit of *mg/L*

PtGA = patient's global assessment of disease activity on a 0-100 VAS

Higher DAS28(CRP) value indicates more severe disease activity.

DAS28(CRP) will be calculated only for the time points with all measurements available.

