### **6.2.3. Analysis of the Primary Efficacy Endpoint**

Change from baseline in DAS28(CRP) at Week 12 will be analyzed using a mixed-effects model for repeated measures (MMRM) approach. The model will include the fixed effects of treatment, visit, treatment by visit interaction, and baseline DAS28(CRP) value. Subjects will be included as a random effect. Missing change scores (eg, due to early withdrawal, etc.) will not be otherwise imputed using the MMRM approach. An unstructured variance-covariance matrix for the repeated measures and Kenward-Roger approximation for the denominator degrees of freedom will be used in the mixed-effects model.

From the MMRM approach, estimated differences in mean change from baseline between each of the GS-9876 doses and the placebo group will be presented with 95% confidence intervals (CIs) and p-values. **PPD**

Change from baseline in DAS28(CRP) will be summarized by treatment and visit using descriptive statistics (sample size, mean, SD, median, Q1, Q3, minimum, and maximum). Plots of mean  $\pm$  SD of DAS28(CRP) values and changes from baseline in DAS28(CRP) over time will be presented.

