### **6.3.1. Definition of Secondary Efficacy Endpoints**

#### **6.3.1.1. ACR 20/50/70**

A subject achieves ACR20 response when this subject has

- $\geq 20\%$  improvement from baseline in the tender joint count (TJC68), AND
- $\geq 20\%$  improvement from baseline in the swollen joint count (SJC66), AND

- $\geq 20\%$  improvement from baseline in at least 3 of the following 5 items:
  - 1) Physician's Global Assessment of Disease Activity (PhGA),
  - 2) Patient's Global Assessment of Disease Activity (PtGA),
  - 3) Patient's pain assessment,
  - 4) Patient's assessment of physical function (HAQ-DI) score,
  - 5) C-reactive protein (CRP)

Percent improvement from baseline at a post-baseline visit is calculated as follows for all 7 components mentioned above:

$$([\text{baseline value} - \text{post-baseline value}] / \text{baseline value}) * 100\%$$

If the baseline value is 0 and the post-baseline value is also 0, then the percent improvement from baseline is set to 0. If the baseline value is 0 and the post-baseline value is non-zero then the percent improvement from baseline is set to missing.

In the case that some ACR20 components are missing, the ACR20 assessment will be derived based on the non-missing components. If non-missing components are not sufficient to determine ACR20 response, then the ACR20 response will be considered as missing.

ACR50 and ACR70 are similarly defined as ACR20 above, except the improvement threshold from baseline is 50% and 70%, respectively.

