#### 6.3.2. Analysis Methods for Secondary Efficacy Endpoints

The ACR20 response rates at Week 12 between each of the GS-9876 dosed groups and the placebo group will be compared using a stratified Cochran-Mantel-Haenszel (CMH) chi-square test adjusting for stratification factors in randomization (ie, prior inadequate response to biologic

therapy, yes vs. no; and Geographic region, region 1 vs. region 2 as defined in Section 3.3). The difference in response rates between treatment groups and the corresponding 95% CIs will be presented. The CMH chi-square p-value for testing the superiority of each of the GS-9876 doses as compared to placebo will be provided, as well as the 2-sided 95% exact CI of the ACR20 response rate based on Clopper-Pearson method for each treatment group. Subjects who do not have sufficient measurements to establish efficacy at Week 12 will be considered as failures (ie, non-responder imputation [NRI]). Sensitivity analysis will be conducted by imputing missing components for determining ACR20 as well as early dropouts via the last observation carried forward (LOCF) method.

[figure not shown]
For ACR50 and ACR70 at Week 12, the same CMH approach with NRI as in the analysis of ACR20 described above will be adopted.

The difference in change from baseline in HAQ-DI between each of the GS-9876 dosed groups and the placebo group will be analyzed using a similar MMRM approach as described in Section 6.2.3. The model will include the fixed effects of treatment, visit, treatment by visit interaction, and baseline value. Subjects will be included as a random effect. Missing change scores (eg, due to early withdrawal, etc) will not be otherwise imputed using the MMRM approach.

[figure not shown]
Mean ACR 20/50/70 response rates with NRI will be plotted by treatment and visit. Mean  $\pm$  SD over time will be plotted for each component of ACR 20/50/70.

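### CRP is cut off at last dose + 3 days but the other DAS28(CRP) and ACR components are not, so a fully collected score can be lost or mix two dates

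*SAP*

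**What the plan says.** Section 3.7.2 and Table 3-1 assign observations to visit windows. The Week 12 window runs from Day 72 with no upper end. The table title and the text attach the on-treatment condition to CRP and the safety data only. Thus "CRP, safety laboratory, weight, vital signs, and ECG data collected after last dose date of any study drug + 3 days" are post-treatment: they are labelled FU-Week 4 up to 30 days after last dose and only listed after that. Joint counts, HAQ-DI with pain, PhGA and PtGA go through the same table with no condition on last dose.

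Section 6.1 builds composites one component at a time. Each value is first put into a window. Then comes "Step 2: Within each visit window, select the component data point for analysis", and the selected values are combined. Among several records, "If record collection date/time is known, latest record will be taken". There is no condition that the components share a visit or date. For the LOCF analysis the instruction is "First LOCF all components over all visits, then combine the components as mentioned above".

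For the primary endpoint, Section 6.2.1 states that "DAS28(CRP) will be calculated only for the time points with all measurements available", and Section 6.2.3 that "Missing change scores (eg, due to early withdrawal, etc.) will not be otherwise imputed using the MMRM approach". For ACR20, Section 6.3.1.1 states "If non-missing components are not sufficient to determine ACR20 response, then the ACR20 response will be considered as missing", and Section 6.3.2 adds "Subjects who do not have sufficient measurements to establish efficacy at Week 12 will be considered as failures".

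No section gives a separate timing rule for CRP when it is used as an efficacy component.

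**The concern.** CRP has two roles in this SAP. It is a component of DAS28(CRP) and ACR, and it is also a laboratory test with its own shift table (Section 7.2.4). Section 3.7.2 groups it with the safety data and applies the safety cut to it everywhere. The SAP does separate efficacy from non-efficacy data when choosing among multiple records (Section 6.1 against Section 3.7.3), but not for this cut.

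The primary endpoint therefore follows neither a consistent on-treatment rule nor a consistent rule that uses data regardless of treatment. For a subject assessed more than 3 days after last dose, joints and PtGA count and the CRP from the same visit does not. Such subjects are mainly those who stopped drug early, so the missing or mixed values are tied to discontinuation. Section 6.2.4 plans no sensitivity analysis of the primary endpoint that could show the effect.

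**Working it through.** **The rule as a formula.** A CRP on Day d is eligible only if d ≤ last dose + 3 (Section 3.7.2). Table 3-1 windows: Week 4 is Days 23–43, Week 8 is Days 44–71, Week 12 is Day 72 onward. The other components need only fall in the window.

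**Dated examples (hypothetical subjects).**

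| Last dose | CRP cut-off | Visits | Joints and PtGA used | CRP used | Result |
|---|---|---|---|---|---|
| Day 80 | 80 + 3 = Day 83 | Day 85 | Day 85 | none | Week 12 DAS28(CRP) missing, though fully collected |
| Day 75 | 75 + 3 = Day 78 | Days 74, 85 | Day 85 | Day 74 | Week 12 score from two dates |
| Day 50 | 50 + 3 = Day 53 | Days 50, 57 | Day 57 | Day 50 | Week 8 score from two dates |

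In the first row no other CRP lies in the Week 12 window. Section 6.1 generally allows composites to be derived from the non-missing components, but the specific rule in Section 6.2.1 governs DAS28(CRP), so the score is missing.

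**When the cut applies.** A CRP drawn on nominal Day N is cut if last dose ≤ N − 4: 29 − 4 = Day 25, 57 − 4 = Day 53, 85 − 4 = Day 81. No CRP can enter a window with lower limit L if last dose ≤ L − 4: 23 − 4 = Day 19, 44 − 4 = Day 40, 72 − 4 = Day 68. These limits cost something only if the other components are assessed that long after last dose.

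**Size of the date mixing in DAS28(CRP).** The CRP term is 0.36 ln(CRP + 1). With illustrative values that are not in the SAP:
- 5 against 10 mg/L: 0.36 × ln(11/6) = 0.22
- 5 against 20 mg/L: 0.36 × ln(21/6) = 0.45

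One such subject in an arm of 20 moves the arm mean by 0.218/20 = 0.01 to 0.451/20 = 0.02. The planned difference is 1.2 (Section 1.3), so this is trivial.

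**ACR20 when no CRP remains in the window.** Assume the tender and swollen criteria are met. Of the 2^5 = 32 improved/not-improved patterns on the five items, 10 + 5 + 1 = 16 have at least 3 improved.
- In 10 of the 16, at least 3 of the 4 non-CRP items improved (5 patterns × 2 CRP states). The response is still determined.
- In 6 of the 16, exactly 2 of the 4 improved and CRP improved. With CRP removed the response cannot be determined and is counted as a failure.
- All 16 non-responder patterns remain non-responders or become imputed failures.

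Each converted responder lowers that arm's rate by 1/20 = 5 percentage points. The 6 of 16 counts patterns; it is not a probability.

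**ACR20 when an older CRP is substituted.** Nothing is missing, so non-responder imputation does not apply. Take exactly 2 of the 4 non-CRP items improved. If the visit CRP improved and the older one did not, a responder becomes a non-responder. If the older CRP improved and the visit CRP did not, a non-responder becomes a responder.

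**LOCF sensitivity analysis.** An earlier CRP is carried forward in place of one that was measured at the visit.

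**The plan's power figure.** The stated 78% reproduces: noncentrality 1.2/(1.35 × √(2/20)) = 2.81 on 38 degrees of freedom gives 78.2%. This point does not alter it.

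**The case against.** The best reply is that few or no subjects may be exposed. Section 4.1 counts completion of drug separately from completion of study, but that does not show that efficacy visits continue after drug is stopped. Section 1.2 gives 4 weeks of follow-up after last dose. If assessments end there, a subject with last dose by Day 43 has no record of any component from Day 72 on (43 + 28 = 71), and the cut costs that subject nothing at Week 12. The FU-Week 4 label is given only to CRP, safety laboratory, weight, vital signs and ECG. That fits with joints and globals not being assessed at follow-up, though it does not prove it. This stands: exposure is unknown. It does not cure the rule, because the cut depends on last dose and not on the follow-up visit. Any assessment in a window more than 3 days after last dose triggers it.

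A second reply is that the cut has a use. With an open-ended Week 12 window and the latest record taken, an uncut follow-up CRP could replace the Week 12 value. This also stands, and it rules out simply exempting CRP.

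A reader might infer that the rule biases ACR20 in one direction only. That holds only where no CRP is left in the window. A reader might also infer that everyone with last dose by Day 68 loses a Week 12 score, or that completers with a slightly late visit do. The first needs efficacy assessments to continue off drug. The second needs dosing to stop before the late visit. The SAP states neither.

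**Conclusion.** The point holds as a minor one. Followed as written, Sections 3.7.2, 6.1 and 6.2.1 can void a DAS28(CRP) whose four components were all collected, or combine components from two dates. No other section corrects this.

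For ACR20 the error runs against response when no CRP remains in the window, and in either direction when an older CRP is substituted. Per exposed subject the cost is one lost or mixed DAS28(CRP), or at most 5 percentage points on an arm's ACR20 rate with 20 per arm.

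The number exposed cannot be computed from the SAP and may be small or nil, because it depends on which efficacy assessments are made after drug is stopped. A reader might infer a loss of power or a materially biased primary result; the document gives no figure that would support either.

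**What to change.** In Sections 3.7.2 and 6.1, state one timing rule for all components of DAS28(CRP) and ACR, chosen before unblinding to match the intended estimand. Either:

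1. apply the last dose + 3 days limit to every component; or
2. exempt CRP as an efficacy component from that limit, keep the limit for the safety-laboratory summaries, and at the same time keep post-treatment follow-up records of every component out of the open-ended Week 12 window.

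Under either option, take CRP from the same visit as the selected joint counts and PtGA, and allow a prompt redraw when a sample is unusable (Section 7.2 already excludes haemolysed results from the laboratory analysis).

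The cost is SAP wording and derivation programming; no new data or visits are needed. Option 1 drops some off-drug scores, option 2 keeps them, and same-visit matching may lose a few scores under both.
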